# 6.2.2 STAGE 1 STEP 2 - Expand Current and Future DLs to 3 Patients

The cohort size increases from 1 to 3 patients with 2 additional patients added to the current cohort. A minimum of 21 days must separate each dose cohort. Continue dose escalation until:

- 1st DLT event Activate Stage 2 in Section 6.2.3.

  OR
- 9 patients are treated at the DL4 This completes enrollment and Stage 2 is not used.

# 6.2.3 STAGE 2 Continual Reassessment Method (CRM)

The study design changes to an application of the continual reassessment method (CRM). Enrollment occurs in cohorts of three with a minimum of 14 days between the 1st and 2nd patient. Each new cohort of three patients are sequentially assigned to the most appropriate dose by the study statistician based on the updated toxicity probabilities once the 3rd patient in a cohort reaches Day 21 (DLT period). The goal will be to identify one of the 4 dose level strategies corresponding to the desired maximum toxicity rate of ≤25%. The MTD will be identified by the minimum of the following criteria: (1) the total Stage 2 sample size of 24 is exhausted or (2) 9 consecutive patients are enrolled at the same dose.

### 6.3 Monitoring for Dose Limiting Toxicities and Excessive Toxicity

Toxicity and adverse events are classified and graded according to NCI's Common Terminology Criteria for Adverse Events V 5.0 (CTCAE) unless otherwise noted in Section 10.

Note during the fast-track dose escalation only (Stage 1, Step 1), patients also are monitored for the pre-defined treatment emergent events defined in Section 6.2.1.

**Dose Limiting Toxicity (DLT)** is defined as any of the following treatment emergent adverse events using the NCI Common Terminology Criteria for Adverse Events (CTCAE) Version 5.0 within the 21 days after the 1st dose of HCW9218:

DLT event	Exceptions:		
Any Grade 3 or Grade 4 febrile neutropenia Any Grade 3 thrombocytopenia with bleeding Any Grade 3 or higher non-hematologic adverse event	
 
Grade 4 lymphopenia hat resolves to Grade 1 or lower (or to Baseline or lower, if pre-existing Grade 2 or higher) within 7 days
 
Grade 4 leukopenia that resolves to Grade 1 or lower (or to Baseline or lower, if pre-existing Grade 2 or higher) within 7 days
 
Grade 3 nausea, vomiting and/or diarrhea that last < 72 hours
 
Grade 3 or higher electrolyte abnormality that lasts < 72 hours, is not clinically complicated, and resolves spontaneously or responds to conventional medical interventions
 
Isolated Grade 3 elevation of ALT and/or AST that resolves to Grade 1 or lower (or to Baseline or lower, if pre-existing Grade 2 or higher) within 7 days
 
Grade 3 amylase or lipase that is not associated with symptoms or clinical manifestations of pancreatitis
 
		
	
 
Grade 3 fatigue, not due to disease progression, that lasts < 1 week
 
		
Hy's Law case (i.e., alanine aminotransferase/ aspartate aminotransferase (ALT/AST) >3 x ULN in combination with total bilirubin level (TBL) > 2 x ULN in the absence of cholestatic injury (ALP < 2 x ULN (Ricart, 2017; FDA, 2009)) and no other cause identified) after excluding biliary tract obstruction and liver metastasis  Inability to receive Cycle 2 dosing due to treatment related toxicity	MORE - I WOR		

The Dose Limiting Toxicity (DLT) Observation Period is defined as 21 days after the first dose of HCW9218. The DLT period does not end until the patient is assessed on Cycle 2 Day 1 (+3 days) and the results of lab work drawn on Cycle 2 Day 1 (+3 days) confirms no new DLTs since the previous assessment.

# Monitoring for Excessive DLT's (Stage 2 patients only):

A stopping rule is in place to stop the trial in case there are excessive DLTs based on Monitoring Guidelines in place for excessive toxicity. At the end of the 21-day DLT period for each cohort of patients, the study statistician or designee updates posterior probability that the lowest dose is unacceptably toxic. Refer to Section 13.4 for complete details.

# 6.4 Supportive Care and Concomitant Medications

Supportive care will be provided per institutional guidelines. Guidelines may be updated based on current data/drugs without requiring a protocol amendment or be considered a protocol deviation.

If a rash occurs and the rash area surrounding the HCW9218 injection site is > 6 cm and symptomatic (painful and/or itchy), it may be treated (at the discretion of the treating physician) with topical 0.05% clobetasol propionate (i.e., 0.05% Cormax) or 0.1% triamcinolone (i.e., Kenalog) cream.

Diphenhydramine may be administered pre- (25-50 mg TID orally) and post-dosing  $(25-50 \text{ mg TID orally } \times 2 \text{ days})$  of HCW9218 at the discretion of the treating physician. Diphenhydramine should be eliminated if not tolerated.

Red blood cell and/or platelet transfusions can be administered as clinically indicated.

Palliative "standard of care" radiation therapy is permitted to non-target tumor(s) such as bony lesions at the discretion of the treating investigator.

# 6.5 Prohibited Concomitant Therapy

Unless the patient discontinues the study treatment, no investigational or commercial anti-cancer agents or anti-cancer therapies other than HCW9218 and supportive care therapies (i.e., topical steroids) may be administered. Palliative radiation therapy is permitted as described in Section 6.4.

The use of systemic corticosteroids medications may result in loss of therapeutic effects of the investigational product and should be avoided; however, in the event of a life-threatening inflammatory reaction to HCW9218, the administration of dexamethasone or other corticosteroids-based medication is warranted. Prednisone should be avoided, with the exception of use in patients with CT contrast allergies.

Certain cytokines, including IL-2 and TGF-β, have been found to suppress the activities of cytochrome P450 enzymes. This may potentially indirectly affect the metabolism of other medications resulting in significant toxicities in some cases. Since the effects of HCW9218 on human cytochrome P450 enzymes are not yet known, use of cyclosporine, statins, or warfarin (Coumadin) should be avoided in participants receiving HCW9218.

# 6.6 Duration of Study Treatment

A minimum of two treatment cycles is planned and HCW9218 may continue until disease progression unless any one of the following occurs sooner:

- Patient requests to discontinue treatment early if in agreement, follow-up would continue as in Section 6.7 unless the patient also withdraws consent.
- In the judgement of the treating Investigator and documented in the medical record, study treatment is no longer in the best interest of the participant.

An End of Treatment (EOT) visit occurs 3 weeks (±1 week) after the last dose of HCW9218 to confirm no ongoing side effects/toxicity. If ongoing toxicity at the EOT visit, it should be managed as medically appropriate and documented, it if meets the criteria for documenting as an AE be followed until resolution or stabilization.

In the situation where a patient's EOT visit falls outside of the visit window due to a prolonged period before the decision to discontinue treatment is made, the EOT related activities may be retrospectively abstracted from the medical record from around the time the EOT would have occurred and/or delayed until the next standard of care visit. Missing items / research samples will not be considered a deviation.

# 6.7 Follow-Up for Disease Response and Survival (Duration of Study Participation)

After the End of Treatment visit follow up continues for 12 months from the 1st dose of HCW9218 to fulfill the secondary endpoints of disease status at 3, 6 and 12 months and progression free survival / overall survival at 6 and 12 months.

If a patient discontinued treatment for a reason other than disease progression, disease status is documented per standard of care reassessments until progression, and then for survival only until the end of the 12 month follow-up period.

Follow-up assessments may be in person, by medical record review, or local medical doctor if patient is no longer seen at the treating institution. In person follow-up visits solely for this research study are not required and may be linked with a standard of care visit. Refer to Section 8 for allowable time related windows around each follow-up time points.

Follow-up may end early if any of the following apply:

- The patient is discharged to hospice
- The patient withdraws consent
- The patient is lost to follow-up (defined as 3 missed appointments/attempts to contact)

If a patient dies before the end of the study defined follow-up, record the date of death as the off-study date and reason off study as death and add the date of death. Refer to Section 10.3 regarding reporting of deaths while a patient is on study.

If a person ends follow-up before the 12 month study period (i.e. withdraws consent, lost to follow-up), public records will be searched for survival information for the endpoints of survival at 6 and 12 months.

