# 12.2 Secondary Endpoints

The safety of repeat dosing of HCW9218 is adverse events (AEs) based on CTCAE v5.

Response and progression endpoints are based on the Response Evaluation Criteria in Solid Tumors (RECIST) 1.1.

- Response rate (CR, PR or SD) at 3 months, 6 months and 12 months
- Progression-free survival (PFS) by 6 month and 1 year is defined as the duration of time from start of treatment to time of progression or death, whichever occurs first
- Overall survival (OS) at 6 month and 1 year from 1st dose of HCW9218 is defined as patients alive at 1 year

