# **Secondary Endpoints**

If there are sufficient numbers, the secondary endpoints of overall survival and progression-free survival by 6 months and 1 year will be estimated with Kaplan-Meier curves. The primary efficacy endpoint of response rate will be estimated by a simple proportion with 95% confidence limits if sufficient numbers exist. Safety will be estimated by the proportion of adverse events based on CTCAE v5. Further descriptive statistics and plots such as boxplots, spaghetti plots and swimmer plots will be used to assess kinetics and other markers of efficacy such as immune based monitoring and toxicity.

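### Follow-up may end at hospice discharge and no PFS rule covers it; if patients without documented progression are censored there, Kaplan-Meier PFS is biased upward

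*Combined protocol and SAP*

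**What the plan says.** Section 6.7 sets up follow-up to 12 months from the first dose, in order to supply disease status, PFS and OS. For a patient who stops treatment without progression, "disease status is documented per standard of care reassessments until progression", and survival alone is followed after that. The section then states "Follow-up may end early if any of the following apply" and gives three reasons. The first is "The patient is discharged to hospice"; the others are withdrawal of consent and loss to follow-up.

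One sentence deals with recovering data after an early exit. It opens "If a person ends follow-up before the 12 month study period (i.e. withdraws consent, lost to follow-up", closes the parenthesis there, and continues "public records will be searched for survival information for the endpoints of survival at 6 and 12 months". It mentions neither hospice nor PFS.

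Section 12.2 bases progression on RECIST 1.1 and defines PFS as "the duration of time from start of treatment to time of progression or death, whichever occurs first". Section 13.2 says that OS and PFS at 6 months and 1 year "will be estimated with Kaplan-Meier curves", provided numbers are sufficient. There is no PFS censoring rule, no provision that counts clinical decline as a PFS event, and no sensitivity analysis. Appendix III labels patients who stop treatment because of declining health, without objective progression, as having symptomatic deterioration. It asks for efforts to document progression afterwards, but does not connect the label to PFS.

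**The concern.** Kaplan-Meier is valid only if patients who are censored have the same outlook as those who stay at risk. Discharge to hospice is close to the opposite: it marks failing disease. A patient whose progression was documented before hospice already has a PFS event and is not affected. The exposed group is those who enter hospice with no documented RECIST progression.

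That group is plausible here. Patients have failed at least two prior lines (Section 4.1.1), imaging may be as infrequent as every 12 weeks (Section 8), and treatment may stop on the investigator's judgement without progression (Section 6.6). After that, disease status depends on standard-of-care reassessments, which a hospice patient is unlikely to have.

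With no event recorded, follow-up closed and no rule to the contrary, the usual handling is to censor at last contact. Appendix III treats early deaths and unassessable patients as failures for response rate. The same patient could therefore count as a failure for response and leave the PFS risk set as though nothing had happened. With 12 to 24 patients in all, a few such cases would visibly change the PFS estimate that is carried forward to later studies.

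**Working it through.** The plan states no PFS or OS rate, median, event count or dropout rate, so there is no figure to reproduce. The two calculations below show direction and scale only. Apart from the sample size of 12 to 24 (synopsis, enrollment goal) and the 12-week scan interval (Section 8), their inputs are assumptions.

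**Hand illustration.** Assume 24 patients, of whom 4 enter hospice at day 60 without a scan. Assume about two-thirds of the rest progress at the 12-week scan, with no further events up to 6 months.

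- Four censored: 20 are at risk at the scan and 13 progress, so PFS at 6 months = 7/20 = 35.0%.
- Four counted as failures: 20/24 × 7/20 = 7/24 = 29.2%. The difference is 5.8 points.
- With 6 such patients, 12 of the remaining 18 progress: 6/18 = 33.3% against 6/24 = 25.0%. The difference is 8.3 points.

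**General form.** Let h be the share of true PFS failures that are hospice entries without a scan, censored at that moment. If h is constant over time, the Kaplan-Meier estimate tends to S(t)^(1−h) instead of S(t). With an assumed exponential PFS and a median of 3 months, S(6) = 0.5^(6/3) = 25.0% and S(12) = 0.5^(12/3) = 6.25%. For h = 20%, 0.25^0.8 = 33.0% at 6 months.

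A simulation (4,000 trials per setting, n = 24, continuous observation, mean of 1 month from hospice entry to death) compared three rules:

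- A: censored at hospice entry.
- B: the death found in records is the PFS event.
- C: hospice entry itself is the PFS event.

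| h | A, 6 mo | A, 12 mo | B, 6 mo | B, 12 mo | C, 6 mo | C, 12 mo |
|---|---|---|---|---|---|---|
| 10% | 28.5% | 8.4% | 25.5% | 6.5% | 24.8% | 6.3% |
| 20% | 33.0% | 11.0% | 26.5% | 6.7% | 25.0% | 6.3% |
| 30% | 38.0% | 14.7% | 27.5% | 7.0% | 25.3% | 6.4% |
| 40% | 43.7% | 19.5% | 28.0% | 7.1% | 25.1% | 6.3% |

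Over assumed medians of 2 to 4 months and h of 10% to 40%, the bias at n = 24 is:

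- Rule A: about +3 to +19 points at 6 months and +1 to +16 points at 12 months.
- Rule B: about +0.5 to +3 points at 6 months and 1 point or less at 12 months. The remainder arises because the event is dated at death, somewhat after the decline.
- Rule C: none, by construction, since hospice entry is taken as the moment of failure.

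Results at n = 12 are similar. The plan does not say which rule applies.

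**The case against.** A reader might infer that these patients are censored, that PFS cannot be repaired at all, and that both Kaplan-Meier curves are therefore biased upward. The documents do not support that.

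- Ending follow-up at hospice is permitted, not required, and no text says that such patients are censored. Censoring is the default reading of a silence.
- The search sentence applies to anyone who ends follow-up before 12 months, and hospice is one of the three early exits listed just above it. The protocol uses i.e. loosely elsewhere to introduce examples, as with scheduling issues in Section 8. Read this way, the search covers hospice patients and OS is largely protected.
- Death is a PFS event, so a death date found for OS is also PFS information, and nothing bars its use.
- Other text captures deaths: the event table in Section 10.2 documents any death, with date and cause, through 12 months upon knowledge; Section 8.1 schedules survival follow-up every 3 months; and Section 6.7 allows record review or contact with a local physician.
- Appendix III asks for progression to be documented after treatment stops, and scans may come sooner than 12 weeks.
- The hand illustration has no source for its 4 or 6 patients. Its 5.8-point gap is about 1.4 patients (0.058 × 24), while the exact 95% interval for 7/24 is about 13% to 51%.
- PFS is secondary and descriptive, estimated only if numbers suffice, and drives no dose decision.

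All of this stands, and it limits the point to a conditional one about PFS. It does not remove the point. The safeguards are discretionary or passive, the search names only survival, and none of them tells the analyst how to treat a hospice patient without documented progression.

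**Conclusion.** The point holds in conditional form. Section 6.7 lets follow-up end at an event tied to failing disease, and the plan does not say how PFS is then handled. If patients without documented RECIST progression are censored at hospice entry, PFS at 6 and 12 months is overstated. If deaths found in records are used as PFS events, most of the bias disappears in the illustration.

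The direction is certain only under the first rule. The size cannot be determined from the documents, because the ranges above depend on the assumed median, the assumed share of failures and the assumed time from hospice entry to death. An upward bias in OS should not be claimed if the search is read to cover all early exits. The MTD is unaffected. This is a worthwhile low-cost correction to a secondary endpoint.

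**What to change.** - **Section 6.7, reasons for ending follow-up:** remove hospice discharge as a reason to end vital-status follow-up. Continue by record review or local physician contact, which the section already allows.
- **Section 6.7, records search:** name hospice alongside withdrawal and loss to follow-up, and state that the result serves PFS as well as OS.
- **Sections 12.2 and 13.2:** count any death found within 12 months of the first dose as a PFS event when no progression was documented earlier, and state the censoring rule for everyone else.
- **Section 13.2:** add one sensitivity analysis that counts hospice entry for clinical decline (symptomatic deterioration in the sense of Appendix III) as a PFS event on that date.

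The cost is a short amendment and a few extra record checks, with no added visits. The PFS figure may come out slightly less favourable.

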# 7 HCW9218 Potential Toxicities and Management

#### 7.1 Clinical Profile

The adverse event (AE) profile of HCW9218 has not yet been evaluated in human subjects.

The HCW9218 protein complex comprises an IL-15 domain, which is a common γ chain cytokine that may have similar immunostimulatory properties as IL-2. HCW9218 treatment, particularly at high-dose levels, could potentially cause similar side effects, including severe cytokine release syndrome or capillary leak syndrome, as commercially available IL-2, Proleukin® (Clinigen, Inc. Yardley, PA) that is approved for use at high doses in advanced melanoma and advanced renal cell carcinoma. Therefore, in general, the Investigator may refer to the approved product package insert for Proleukin® (aldesleukin) for Injection and other published literature describing the management of IL-2-related AEs (Dutcher et al, 2014). Details of these AEs are provided in Appendix II.

Additionally, expected AEs based on the published clinical experience of monotherapy with the related product candidates, including recombinant human IL-15 (rhIL-15) (Conlon et al, 2019; Miller et al, 2018; Conlon et al, 2015), IL-15 mutein/IL-15R $\alpha$ Su-Fc complex (ALT-803, nogapendekin alfa inbakicept) (Margolin et al, 2018; Romee et al, 2018), TGF $\beta$ RII-Fc fusion (AVID200) (Lafyatis et al, 2020; Mascarenhas et al, 2020; Yap et al, 2020) and TGF $\beta$ RII-anti-PD-L1 IgG1 fusion (M7824, bintrafusp alfa) (Tan et al, 2021; Khasraw et al, 2021; Kang et al, 2020; Strauss et al, 2020), are provided in Appendix II. These agents contain protein domains that are similar to those of HCW9218. Information on the AEs reported in clinical studies of anti-TGF- $\beta$  antibody therapy (Lacouture et al, 2015; Morris et al, 2014), assumed to have a similar mechanism-of-action as the HCW9218 TGF $\beta$ RII domain, also is included in Appendix II.

In general, treatment with ALT-803 monotherapy at up to 0.02 mg/kg was well-tolerated and no DLTs were reported. Dose-dependent transient flu-like constitutional AEs were observed following i.v. administration whereas s.c. delivery resulted in self-limited injection site rashes infiltrated with lymphocytes without acute constitutional symptoms. Treatment with immunotherapies

containing the TGF $\beta$ RII domain were also well-tolerated at i.v. dose levels up to 15 mg/kg with reported treatment-emergent skin lesions and mucosal bleeding being associated with TGF- $\beta$  inhibition. The combination of IL-15 immunostimulatory and TGF- $\beta$  antagonist activities in HCW9218 may result in additional and/or more frequent or severe AEs.

# 7.2 Most Common and Most Serious Side Effects Seen In Drugs Similar To HCW9218

HCW9128 has not yet been evaluated in human clinical studies. Thus, the expected AEs are based on the published clinical experience with other related immunotherapies, including recombinant human IL-2, recombinant human IL-15, TGFβRII-Fc fusion and anti-TGF-β antibody.

All adverse events listed in Appendix II are defined as "Expected" for the purpose of event documentation and reporting requirements.

The tables below show the most common and most serious side effects seen in drugs similar to HCW9218. This language matches the treatment consent form.

COMMON, SOME MAY BE SERIOUS In 100 people receiving a drug similar to HCW9218, more than 20 and up to 100 may have:	OCCASSIONAL, SOME MAY BE SERIOUS In 100 people receiving a drug similar to HCW9218, from 4 – 20 people may have:	RARE, AND SERIOUS In 100 people receiving a drug similar to HCW9218, 3 or fewer may have:

 
redness, itching and pain or swelling at the injection site
 
infection, especially when white blood cell count is low
 
anemia, which may require a blood transfusion
 
bruising, bleeding
 
nose-bleed
 
fever, chills, pain
 
flu like symptoms
 
swelling in arms and legs
 
pain in belly
 
pain in joints
 
loss of appetite
 
diarrhea
 
dizziness
 
shortness of breath
 
	
 
chest pain
 
skin rash
 
abnormal eye movement
 
constipation
 
bloating
 
cough
 
headache
 
sores in mouth
 
depression
 
anxiety/ worry
 
extreme sleepiness
 
weight gain
 
abnormal heartbeat
 
blurred vision
 
	
 
skin lesions
 
allergic reaction
 
fluid in the organs
 
heart attack
 
internal bleeding
 
severe blood infection
 
damage to multiple organs, heart, kidney, liver, others
 
swelling, tenderness and/or redness of the veins
 
stroke
 

COMMON, SOME MAY BE SERIOUS In 100 people receiving a drug similar to HCW9218, more than 20 and up to 100 may have:	OCCASSIONAL, SOME MAY BE SERIOUS In 100 people receiving a drug similar to HCW9218, from 4 – 20 people may have:	RARE, AND SERIOUS In 100 people receiving a drug similar to HCW9218, 3 or fewer may have:

 
fatigue/ tiredness
 
high blood pressure which may cause headaches
 
increase/ decrease in urination
 
drop in blood pressure
 
itching
 
dry skin
 
nausea, vomiting
 
abnormal lab results
 
blood clot
 
confusion
 
		

